#### 3.4.2 Description of Procedures

- Medical history: a review of treatment history, any ongoing medical conditions, and medical history pertaining to eligibility on study and involvement during the study.
- Physical exam: review of organ systems, weight, and vital signs (i.e., temperature, pulse, respirations, blood pressure, and oxygen saturation). After initiation of study drug, symptom-directed physical examinations will be performed as clinically indicated in the investigator's judgment. Note: Height will only be required prior to treatment no later than Cycle 1 Day 1.
- Performance status (ECOG and Karnofsky): an assessment of activities of daily living; see [Appendix A](#).
- Laboratory assessments: the following comprises the required tests/analytes. These assessments may be performed at Clinical Laboratory Improvement Amendments (CLIA) (or equivalent) certified laboratories outside the enrolling site and results forwarded to the study team for review and management. Given that the methodologies utilized are similar

across all laboratories, no significant variability is expected and there is no anticipation that study data will be affected.

However, as different laboratories use slightly different kinds of equipment, each laboratory must determine/validate its own reference ranges. Therefore, on this protocol, normal ranges from each lab will be used in reference to terms such as ULN, except in cases where absolute values are appropriate and are specified as such. Note: Panels containing the tests below may be ordered in lieu of individual tests.

- CBC with differential: includes Neutrophils, Lymphocytes, Monocytes, Eosinophils, Basophils, WBC, RBC, Hemoglobin, Hematocrit, RBC Indices, MCV, RDW, Platelet.
- Blood chemistries: includes Sodium (Na), Potassium (K), Chloride (Cl), Total CO2 (bicarbonate), Creatinine, Glucose, Urea nitrogen (BUN), Albumin, Calcium total, Magnesium total (Mg), Inorganic Phosphorus, Alkaline Phosphatase, ALT/GPT, AST/GOT, Total Bilirubin, Direct Bilirubin, Total Protein will be performed to assess organ function for safety
- HIV, HBV, HCV – infectious disease serologies as per section [2.2.2](#)
- Vitamin B12, Folate, copper, zinc, TSH, free T4- to assess alternative/reversible causes of cytopenias that may confound MDS diagnosis at screening
- Reticulocyte count
- Urinalysis: for safety
- Serum or urine pregnancy test: performed prior to administration of study therapy in individuals of childbearing potential (see Section [2.1.1.5](#))
- Electrocardiogram: 12-lead ECGs will be performed to assess cardiac activity
- Bone marrow biopsy and aspiration: to assess response to therapy
- Concomitant medications: a record of all medications including herbal supplements but not including study therapy that a participant has taken during the study will be recorded in order to assess confounding factors in safety and efficacy assessments
- Adverse events: participant reported adverse events will be collected throughout the study in order to assess safety.
- TBNK: for immunologic phenotyping
- Study drug administration, including dispensing and adherence review: Study drug will be dispensed at each cycle and instructed to be self-administered by participants, unless otherwise described, per schedule – see Section [3.1.4](#). Participants will be given a dosing diary (see [Appendix K](#)) to be reviewed at each noted visit for drug adherence/accountability.

### 3.4.3 Correlative/Exploratory Assessments

- Research blood and tissue samples: refer to Section [5](#).
- Clinician tools:

- **Rockwood Frailty Index (Appendix E):** The Rockwood Clinical Frailty Score (CFS) was developed as a deployable tool to be used by clinicians to assess level of vulnerability. It uses clinical descriptors and pictographs to divide participants into 9 levels of vulnerability ranging from 1 (very fit) to 9 (terminally ill). (46) This 9-point scale uses a visual chart to assess frailty classifications; someone with a score of  $\geq 5$  is classified as frail. The CFS was validated in a sample of 2305 older Canadian participants who remained alive 5 years after the Canadian Study of Health and Aging (CSHA-2). (47) CFS will be completed in a clinical setting. A member of the study team will observe the participants physical activity and ability and score them.
- **MDS-CI (Appendix F):** MDS-specific comorbidity index (MDS-CI) is a scoring system for MDS participants to be used by clinicians using a time-dependent index to predict the effects of comorbidities on treatment outcomes. (48) Five comorbidities independently predictive for non-leukemic death (cardiac, hepatic, pulmonary, renal, solid tumor) were assigned a score proportional to the regression coefficient of the multivariable Cox's proportional hazards model, the MDS-CI score was calculated as the sum of these weighted scores, and grouped into three risk groups – low, intermediate, and high risk. The MDS-CI was validated in a sample of 840 MDS participants from Pavia, Italy and a validation cohort of 504 participants in Dusseldorf, Germany. (49) A member of the study team will assess clinical information and score by completing the standard form.
- Patient-reported outcomes (PROs): The following PROs will be administered on this study (electronically via a CCR-approved system – Scribe; which is not yet 21 CFR 11 validated, however certification is currently being pursued). Participant questionnaires are only offered in English and are therefore not required in non-English speaking participants that may be enrolled on the protocol
  - **European Organization for Research and Treatment of Cancer (EORTC) quality of life questionnaire = EORTC QLQC30 score** (see Study Instrument packet and [Appendix G](#)): The European Organization for Research and Treatment of Cancer (EORTC) Quality of Life Questionnaire is a participant self-report questionnaire used to assess participants' health-related quality of life in the oncology field. (50) This questionnaire incorporates nine multi-item scales, three symptom scales, a global health scale, and a quality-of-life scale. This questionnaire was validated across three language-cultural groups as well as against different questionnaires. (51) EORTC QLQ-C30 has been the most frequently used participant-reported outcome (PRO)/quality of life questionnaire in published MDS studies to-date and has commonly been a contributory measure of PRO to drug-approval processes for MDS. (52) This questionnaire takes approximately 15 minutes to complete. This will be completed at baseline, at response evaluation, at disease progression, at the end of treatment and post therapy follow-up.
  - **NIH MDS Adult Psychosocial Assessment** (see Study Instrument packet/ [Appendix H](#)): The psychosocial assessment is a self-report form that was originally developed for the NIH gastrointestinal stromal tumor (GIST) Clinic(53) in order to identify specific psychosocial areas of concern and symptoms not covered in the Patient-Reported Outcomes Measurement Information System (PROMIS) and

other standardized measures. It contains items covering demographic factors, perceived general health, psychosocial concerns, psychiatric history, self-identified needs, and interest in a range of possible psychosocial services. It has now been adapted and is being used with participants at the NIH participating in the Medullary Thyroid Cancer (MTC) and RUNX1 natural history studies. This questionnaire takes approximately 10 minutes to complete.

- **PRO-CTCAE** (see Study Instrument packet/[Appendix H](#)): The PRO-CTCAE is a participant-reported outcome measurement system developed by the NIH to capture the symptomatic adverse events in participants on cancer clinical trials [1]. It was designed as a companion to the Common Terminology Criteria for Adverse Event (CTCAE), which is often used per medical professionals' evaluation. This instrument will allow us to select, but not be limited to the symptoms that are anticipated based on the previous experiences. It can be a flexible tool for descriptive reporting system, which participants can complete at their own convenience. It also can be used in conjunction with the CTCAE to provide a better understanding of the toxicities of the clinical trial treatments. The PRO-CTCAE predetermined symptoms will consist of 15 symptoms and additional five open text boxes for participants to also add additional symptoms they may be experiencing. Completion of this instrument will take 3-4 minutes on average to complete. This will be completed at baseline, weekly for the first two cycles, at response evaluation, at disease progression, at the end of treatment and post therapy follow-up.
- **PROMIS Physical Function Short Form 10B** (see Study Instrument packet/[Appendix H](#)): A PROMIS Physical Function (PROMIS-PF) item bank was developed with the goal of measuring a person's ability to carry out various activities that require physical capabilities, ranging from self-care to more vigorous activities that require mobility, strength or endurance [5,6]. The PROMIS Physical Function 10b, a 10-item tool is scored from 1 'unable to do' to 5 'without any difficulty'. Time frame is not provided but current status is inferred. Completion of this instrument will take on average 2-3 minutes. This will be completed at baseline, weekly for the first two cycles, at response evaluation, at disease progression, at the end of treatment and post therapy follow-up.
- **Overall Side Effect Bother** (see Study Instrument packet/[Appendix H](#)): FACIT Measurement System Item GP5 'I am bothered by the side effects of treatment', is a single item summary index of bother that has demonstrated association with clinician-reported adverse events and with participants' ability to enjoy their lives that can help to adjudicate the variability in adverse effects across treatments being compared with each other [7]. Completion of this item will take less than a minute. This will be completed weekly for the first two cycles, at response evaluation, at disease progression, at the end of treatment and post therapy follow-up.
- **Patient Global Impression of Severity (PGI-S)** (see Study Instrument packet/[Appendix H](#)): The Patient Global Impression of Severity (PGI-S) is a global index that may be used to rate the severity of a specific condition (a single-state scale). It is a simple, direct, easy to use scale that is intuitively understandable to clinicians. It has been validated in studies of incontinence [8]

and insomnia[9]. For this study, we will ask participants to rate the severity of their symptoms using a 5-point scale (0-none, 1-mild, 2-moderate, 3-severe, 4-very severe) that will take less than a minute on average to complete. This will be completed at baseline, weekly for the first two cycles, at response evaluation, at disease progression, at the end of treatment and post therapy follow-up.

- **Patient Global Impression of Change (PGI-C)** (see Study Instrument packet/[Appendix H](#)): Patient Global Impression of Change (PGI-C) aims to quantify disease activity relative to an anchor point. Specifically, participants are asked to calculate the difference between their current and previous health state based on a Likert scale. Although PGI-C scales typically comprise between 7 and 11 points which show optimal participant preference, discriminative ability and test-retest ability, they can be tailored to specific conditions and disease parameters as per the clinicians' needs [10]. For this study, we will ask participants to rate their global impression of change in their symptoms since their last visit using a 5-point scale (1-much improved, 2-improved, 3-no change, 4-worse, 5-much worse). Completion of this item will take less than a minute on average. This will be completed weekly for the first two cycles, at response evaluation, at disease progression, at the end of treatment and post therapy follow-up.

### 3.5 STUDY CALENDAR

#### 3.5.1 Phase I and II – Screening & Cycle 1

Procedure	Screening	Baseline	Cycle 1											
			Day 1	Days 2-3	Days 4-5	Day 8	Days 9-12	Days 13-14	Day 15	Days 16-19	Day 20	Day 21	Day 22	Day 23
Window(s):	≤30 days	≤7 days	≤7 days	NA	NA	NA	NA	NA	NA	NA	NA	NA	NA	NA
Histologic confirmation	X													
Medical history	X	X	X											
Physical exam	X	X	X			X			X				X	
Vital signs	X	X	X			X			X				X	
Height	X													
Weight	X	X	X			X			X				X	
Performance score	X	X	X											
CBC/differential	X	X	X			X			X				X	
Reticulocyte count	X	X	X											
Chemistries	X	X	X			X			X				X	
Folate, copper, zinc, TSH, free T4, Vitamin B12	X													
Ferritin, erythropoietin	X	X												
HIV HBV and HBC serologies	X													
Pregnancy test	X	X	X 											
Urinalysis		X	X											
ECG	X	X	X 						X 					
Bone marrow biopsy and aspirate	X 	X 												X 
TBNK panel		X	X											
Next gen seq- myeloid panel	X 	X 												
Correlative research studies (see Section 5.1)		X												X 
PK/PD (see Section 5.1)						X 	X 	X			X 	X	X	
Inqovi administration			X	X	X									
KPT-8602 administration						X	X	X 	X	X	X 	X 		

Procedure	Screening	Baseline	Cycle 1												
			Day 1	Days 2-3	Days 4-5	Day 8	Days 9-12	Days 13-14	Day 15	Days 16-19	Day 20	Day 21	Day 22	Day 23	Day 28
Window(s):	≤30 days	≤7 days	≤7 days	NA	NA	NA	NA	NA	NA	NA	NA	NA	NA	NA	NA
Transfusion dependency assessment			X						X						
Adverse event assessment				X	X	X	X	X	X	X	X	X	X	X	X
Concomitant medications			X	X			X			X		X			
Response Assessment															X
Rockwood/CFS and MDS-CI Questionnaires			X												
PRO: NIH MDS Adult Psychosocial Assessment			X												
PRO: EORTC-QLQC30 			X	X											X
PRO: PRO-CTCAE 			X	X			X			X		X			X
PRO: Overall Side Effect Bother 							X			X		X			X
PRO: PROMIS Physical Function 			X	X			X			X		X			X
PRO: PGI-S 			X	X			X			X		X			X
PRO: PGI-C 							X			X		X			X

Any time prior to enrollment.

Includes temperature, blood pressure, heart rate, respiratory rate, oxygen saturation

Includes sodium, chloride, potassium, CO2, BUN, creatinine, glucose, AST/ALT, alkaline phosphatase, total bilirubin, direct bilirubin, albumin, total protein, magnesium, phosphorous, calcium, LDH, uric acid

To be performed within 24 hrs prior to initiating study treatment, for individuals of childbearing potential.

ECG on C1D1 and C1D15 will be done 2 hours post-dose that day (+/- 20 minutes) for QTc monitoring.

Bone marrow core biopsy will be sent for pathologic evaluation. Bone marrow aspirate will be sent for flow cytometry and additional studies per Section 5.1.

May be performed during screening evaluation if no prior sample is available to pathology review to determine diagnosis; must be done within 30 days prior to treatment initiation.

Must be done within 30 days prior to treatment initiation. If a fresh sample was taken at screening to determine eligibility, and 30 days have not elapsed, then bone marrow biopsy and aspirate will not be repeated at baseline.

Phase I only. Bone marrow biopsy and aspirate and flow cytometry may be done on C1D28 +/- 3 days.

CD3, CD4, CD8, CD19, CD4:CD8 ratio, NK markers clinical panel.

May be performed during screening evaluation or baseline; must be done within 30 days prior to treatment initiation.

May be performed during screening evaluation or baseline; must be done within 30 days prior to treatment initiation.

Phase I only, on day of bone marrow biopsy (which may be done on C1D28 +/- 3 days).

See Section [5.1](#) for detailed PK/PD sampling schedule.

On C1D12, blood samples for PK will be collected for participants receiving KPT-8602 at dose level 1 or dose level -2 only (see Section [5.1](#) for detailed PK/PD sampling schedule).

On C1D21, blood samples for PK will be collected for participants receiving KPT-8602 at dose level 2 or dose level -1 only (see Section [5.1](#) for detailed PK/PD sampling schedule).

HR-MDS cohorts (Cohorts 1 & 2): administer Inqovi orally once daily on Days 1-5 of each 28-day cycle.

Participants receiving KPT-8602 at dose level 2 or dose level -1 only.

Participants receiving KPT-8602 at dose level 2 or dose level -1 only.

Participants receiving KPT-8602 at dose level 2 or dose level -1 only.

PROs administered at baseline need not be repeated at C1D1 if within 7 days.

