## 3 STUDY IMPLEMENTATION

### 3.1 STUDY DESIGN

The study consists of two phases:

- Phase I: Safety evaluation with determination of the recommended phase 2 dose (RP2D) of KPT-8602 in combination with Inqovi, and
- Phase II: Efficacy evaluation of KPT-8602 in combination with Inqovi

Participants will be enrolled into one of two cohorts, depending on the phase of study as follows:

- Phase I:
  - **Cohort 1:** Participants with higher-risk MDS that will be treated with Inqovi for 5 days, followed by KPT-8602 at escalating doses.
- Phase II:
  - **Cohort 2:** Participants with higher-risk MDS that will be treated with Inqovi for 5 days, followed by KPT-8602 at the RP2D.

In Phase I, participants enrolled in Cohort 1 will be treated with Inqovi 35 mg/100 mg daily on Days 1-5 of each 28-day cycle, plus KPT-8602 at the corresponding dose level and schedule..

Dose-escalation will follow a standard 3+3 design (see Section [3.1.2](#)), with DLT assessment during the first 28 days of treatment.

In Phase II, participants enrolled in Cohort 2 will be treated with Inqovi 35 mg/100 mg daily on Days 1-5 of each 28-day cycle, plus KPT-8602 at the RP2D identified in Phase I.

The study drugs will be self-administered by the patient, except on days of PK blood draws.

Participants in Cohorts 1 and 2 are eligible to participate in the study if they have received a minimum of 4 cycles of HMA therapy with inadequate response (failure to achieve at least a PR, or experienced disease progression prior to completing 4 cycles). For participants on HMA therapy with Inqovi prior to enrollment, descriptions of initiation of study therapy refer to initiation of KPT-8602 only. Of note, participants receiving Inqovi prior to enrollment must be on the standard dose (35 mg decitabine and 100 mg cedazuridine) without prior dose-reductions.

In both Phase I and Phase II, participants will continue treatment until disease progression, death, unacceptable toxicities as listed in Section [3.3.2](#), or another off-treatment criterion is met (see Section [3.7.1](#)) as long as no other contraindications to further treatment. Participants that do not achieve at least partial remission following cycle 6 will not receive additional treatment.

Blood samples for correlative research will be collected (Section [5.1](#)). Participants may be admitted on day 8 of cycle 1 for pharmacokinetics (PK) studies to be performed, and on other days if necessary or for convenience.

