### 3.1.2 Dose Escalation

In a phase I/II study (NCT 02649790) that evaluated single agent eltanexor in higher-risk MDS, 2 doses were evaluated: 5 patients received 10 mg and 15 patients received 20 mg, every day for 5 days per week of a 28-day cycle. The majority of patients were aged  $\geq 75$  and all were treated and refractory to hypomethylating agents. None of the patients experienced dose-limiting toxicities (DLTs) and the RP2D for eltanexor was selected as 10 mg given on days 1-5 of each week of a 28-day cycle in HR-MDS (20/28 days). Given the overlap in toxicities, particularly hematologic, between hypomethylating agents and eltanexor, our starting dose was set at 10 mg PO daily on Days 8-12 and Days 15-19 (total of 10 days per 28-day cycle as opposed to 20 days per 28-day cycle in NCT 02649790).

In Phase I, dose escalation will proceed in cohorts of 3-6 participants. The MTD is the dose level at which no more than 1 of up to 6 participants experience DLT during the first cycle (28 days) of treatment, and the dose below that at which at least 2 (of  $\leq 6$ ) participants have DLT as a result of the drug.

Participants in Cohort 1 will be eligible for the DLT evaluation if  $\geq 90\%$  (9 out of 10 doses) of KPT-8602 and  $\geq 80\%$  (4 out of 5 doses) of Inqovi were taken within the DLT period. Participants not evaluable for toxicity, will be replaced in the dose level.

Dose Escalation Schedule	
Dose Level	Dose of KPT-8602
Level -2	5 mg PO daily on Days 8-12 and Days 15-19
Level -1	5 mg PO daily on Days 8-21
Level 1 (starting dose)	10 mg PO daily on Days 8-12 and Days 15-19
Level 2	10 mg PO daily on Days 8-21

Dose escalation will start at dose level 1 and follow the rules outlined in the Table below.

Number of Participants with DLT at a Given Dose Level	Escalation Decision Rule
0 out of 3	Enter up to 3 participants at the next dose level
$\geq 2$	Dose escalation will be stopped. This dose level will be declared the maximally administered dose (highest dose administered). Up to three (3) additional participants will be entered at the next lowest dose level if only 3 participants were treated previously at that dose.

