3.5.2 Phase I and II – Cycle 2 – beyond

Procedure	Cycles 2-3					Cycles $\geq 4$			At Disease Progression	End of Treatment	Post-therapy follow-up 	End of Study
	Day 1	Day 8	Day 15	Day 22	Day 28	Day 1	Day 8	Day 28				
Window(s):	-3 days	$\pm 3$ days	$\pm 3$ days	$\pm 3$ days	$\pm 3$ days	-3 days	$\pm 3$ days	$\pm 3$ days	$\pm 3$ days	$30+7$ days	See note.	
Physical exam	X		X			X				X		
Vital signs 	X		X			X				X		
Height												
Weight	X		X			X				X		
Performance score												
Chemistries 	X		X			X			X	X		
CBC/differential	X		X			X			X	X		
Reticulocyte count	X					X			X	X		
Pregnancy test	X					X						
Urinalysis	X					X				X		
Bone marrow biopsy and aspirate 					X 			X 	X			
TBNK panel 	X					X			X	X		
Peripheral blood flow cytometry									X 			
Next gen seq- myeloid panel					X 			X 	X			
Correlative research studies (see Section 5.1)	X		X 		X 	X		X 	X	X		
Inqovi administration 	X					X						
KPT-8602 administration 		X	X				X					
Response evaluation 	X					X						
Transfusion dependency assessment	X		X			X			X	X		
Adverse event assessment	X	X	X	X	X	X		X	X	X		
Concomitant-medications	X		X			X				X		
PRO: NIH MDS Adult Psychosocial assessment 					X			X		X		
PRO: EORTC-QLQC30 	X				X	X		X	X	X	X	
PRO: PRO-CTCAE 	X	X	X	X	X	X		X	X	X	X	
PRO: Overall Side Effect Bother 					X	X		X	X	X	X	
PRO: PROMIS Physical Function 	X	X	X	X	X	X		X	X	X	X	
PRO: PGI-S 	X	X	X	X	X	X		X	X	X	X	

Procedure	Cycles 2-3					Cycles ≥4			At Disease Progression	End of Treatment	Post-therapy follow-up 	End of Study
	Day 1	Day 8	Day 15	Day 22	Day 28	Day 1	Day 8	Day 28				
Window(s):	-3 days	±3 days	±3 days	±3 days	±3 days	-3 days	±3 days	±3 days	±3 days	30+7 days	See note.	
PRO: PGI-C 					X	X		X	X	X	X	
Survival											X	X

Follow-up will occur via phone call every 3 months (+/- 2 weeks) for the first 24 months, then every 6 months (+/- 4 weeks) for 3 years, then annually for up to 8 years. Overall survival, event-free survival, progression-free survival, and treatment status will be assessed at all timepoints.

Includes temperature, blood pressure, heart rate, respiratory rate, oxygen saturation

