## **17.11 APPENDIX K: PARTICIPANT MEDICATION DIARY**

Cohort 1 and 2 – Medication Diary

Cycle: \_\_\_\_\_ Participant's ID: \_\_\_\_\_

Instructions:

1. Complete one form for each cycle of treatment.
2. You will take Inqovi once daily on Days 1-5 or Days 1-4, Days 1-3 or Day 1, 3 and 5 depending on the dose level you are assigned,
3. The tablet should be taken on an empty stomach, 2 hours before or 2 hours after meals, and at the same time each day.
4. If a dose of Inqovi is missed within 12 hours of the time it was supposed to be taken, it should be taken as soon as possible. If it is past 12 hours, the dose should not be made up. Extend the dosing period by 1 day for every missed dose to complete the total number of daily doses for each cycle.
5. You will take KPT-8602 once daily on Days 8-12 for all dose levels, and possibly on Days 13-21 or on Days 15-19 depending on the dose level you are assigned, during a 28-day cycle.
6. If a dose of KPT-8602 is missed within 12 hours of the time it was supposed to be taken, it should be taken as soon as possible. If it is past 12 hours, the dose should not be made up. Extend the dosing period by 1 day for every missed dose to complete the total number of daily doses for each cycle.
7. If you vomit after taking a dose of KPT-8602 and/or Inqovi, do not retake the dose. Take the next dose of KPT-8602 and/or Inqovi at the regular schedule.
8. If you miss any doses please contact us.
9. Record the date, the number of tablets that you took, and when you took them. If you miss a dose, please record this also below.
10. If you have any comments or notice any side effects, please record them in the 'comments' column.
11. On the days you are being seen in clinic, you must bring in your medication supply from home; however, you should not take your medication until instructed, as the blood draws must be timed with when you take your medication.
12. Please bring this form and your bottles (even it is empty) when you come for your clinic visits.

Day	Date	Study Drug				Comments	
		KPT-8602		INQOVI			
		Time	# of Tablets	Time	# of Tablets		
1		None	None				
2		None	None				
3		None	None				
4		None	None				

Day	Date	Study Drug				Comments	
		KPT-8602		INQOVI			
		Time	# of Tablets	Time	# of Tablets		
5		None	None				
6		None	None	None	None		
7		None	None	None	None		
8				None	None		
9				None	None		
10				None	None		
11				None	None		
12				None	None		
13				None	None		
14				None	None		
15				None	None		
16				None	None		

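### One of the two timed QTc ECGs (C1D1) falls a week before the first KPT-8602 dose, leaving each participant one scheduled ECG after KPT-8602 and none at first exposure

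*Combined protocol and SAP*

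**What the plan says.** The ECG row of the Cycle 1 calendar (Section 3.5.1) has four marks: Screening, Baseline, Day 1 and Day 15. Footnote 5 applies to the last two: "ECG on C1D1 and C1D15 will be done 2 hours post-dose that day (+/- 20 minutes) for QTc monitoring". It does not say which drug's dose starts the 2-hour clock.

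The dosing text is consistent on when each drug is given. For Inqovi, the calendar footnote reads "administer Inqovi orally once daily on Days 1-5 of each 28-day cycle". For KPT-8602, the dose table in Section 3.1.2 gives level 1 as "10 mg PO daily on Days 8-12 and Days 15-19" and level 2 as "10 mg PO daily on Days 8-21"; levels -2 and -1 use the same days at the lower dose. The medication diary (Appendix K) tells participants "You will take KPT-8602 once daily on Days 8-12 for all dose levels" and prints None for KPT-8602 on Days 1 to 7.

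The calendar headed "Phase I and II – Cycle 2 – beyond" (Section 3.5.2) has no ECG row, and so none at progression or end of treatment. The ECG entry in Section 3.4.2 adds no timepoint. Section 3.4.1 leaves the content of unscheduled visits to the investigator.

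**The concern.** The stated purpose of the timed ECGs is QTc monitoring, and Section 2.1.1.4 limits entry to a QTc(F) of 470 ms or less. One of the two timed ECGs cannot show an effect of the investigational drug, because none has been given. On the day of first exposure, C1D8, the participant has serial PK sampling but no ECG.

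The stakes lie in the safety data that drive the design. Treatment-related Grade 3 or higher non-hematologic toxicity in the first 28 days is a DLT, with listed exceptions (Section 3.1.1). DLTs decide the 3+3 escalation, and the phase II Bayesian toxicity monitoring (Section 10.4.4.1) uses the same definition. Scheduled detection of a symptomless QTc change after KPT-8602 rests on one tracing per participant in that window.

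**Working it through.** The plan gives no figure to reproduce, so the check sets the schedules side by side.

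**Inputs.** ECG days and timing: Section 3.5.1, footnote 5. Dosing days: Sections 3.1.2 and 3.3.1, Appendix K. PK times: Section 5.1. Tmax and half-life of KPT-8602: Section 1.2.3.3 (median Tmax 1-3 h, terminal half-life 4-6 h).

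**1. ECG days against KPT-8602 dosing**

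| Day in Cycle 1 | Inqovi | KPT-8602 | Timed ECG | KPT-8602 PK sample |
|---|---|---|---|---|
| 1 | yes | no | yes | no |
| 8 | no | first dose, all levels | no | pre-dose, 1, 2, 3, 4, 8, 24 h |
| 15 | no | yes, all levels | yes | no |

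- Timed ECGs: 2. Timed ECGs after a KPT-8602 dose: 1, at all four dose levels.
- C1D1 precedes the first KPT-8602 dose by 8 - 1 = 7 days.

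**2. KPT-8602 doses taken before the C1D15 dose**

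- Levels 1 and -2: Days 8 to 12, 12 - 8 + 1 = 5 doses.
- Levels 2 and -1: Days 8 to 14, 14 - 8 + 1 = 7 doses.

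**3. Does C1D15 stand in for first exposure?**

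The fraction of a dose left after t hours is 2^(-t/half-life); the accumulation ratio with daily dosing is 1/(1 - 2^(-24/half-life)). Both assume simple first-order decline.

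| Half-life | Left at 24 h | Accumulation ratio | Left at 72 h |
|---|---|---|---|
| 4 h | 2^(-6) = 1.6% | 1.02 | 2^(-18) = 0.0004% |
| 6 h | 2^(-4) = 6.3% | 1.07 | 2^(-12) = 0.024% |

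At levels 1 and -2 the Day 15 dose comes 72 h after the Day 12 dose, so exposure is like that of a first dose. At levels 2 and -1 the Day 15 dose is the eighth consecutive one, with accumulation of at most about 7%. The 2-hour point lies inside the Tmax range. The C1D15 ECG therefore samples near-peak exposure close to that of C1D8, but 7 days later and only once.

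**4. Effect of moving the C1D1 ECG to C1D8**

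ECGs after a KPT-8602 dose go from 1 to 2 per participant. The number on the same day as a 2 h PK sample goes from 0 to 1, at every dose level.

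**5. Age of the reference ECG after the move**

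Baseline may be up to 7 days before treatment starts (Section 3.4.1). Counting from Day 1, it may be up to 7 + 7 = 14 days before C1D8. Section 3.4.1 also lets a screening test within that window serve as baseline, so screening and baseline may be the same ECG.

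**The case against.** The best defense is that little is lost. C1D15 at 2 hours is near peak exposure, and accumulation is slight. C1D8 already has physical examination, vital signs, chemistries and adverse event assessment. The clinical experience summarized in Sections 1.2.3.2 and 14.1.3 describes no QT signal, and neurological toxicity is the only event of special interest (Section 8.1.6). This stands, and it limits the weight of the point.

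C1D1 could also be defended as an ECG on Inqovi without KPT-8602, which might help separate the two drugs. The protocol states no such purpose, but the information is real and the move gives it up.

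Section 3.1 says that, for participants already on Inqovi, "descriptions of initiation of study therapy refer to initiation of KPT-8602 only". This does not rescue C1D1: no dose level gives KPT-8602 before Day 8.

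A reader might infer three stronger things, which the documents do not support:

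- That there is only one post-KPT-8602 ECG in the whole trial. It is one scheduled ECG per participant, and Section 3.4.1 allows more at unscheduled visits.
- That the absence of PK on C1D15 breaks an analysis. No objective or endpoint in Sections 1.1 or 10.1 relates concentration to QTc.
- That the entry limit shows a known QT effect. A limit of 470 ms does not establish one.

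**Conclusion.** The point holds as a scheduling mismatch of moderate weight. One of the two timed QTc ECGs is taken 7 days before KPT-8602 starts, and each participant has one scheduled ECG after the drug, preceded by 5 or 7 doses. The loss is a first-exposure ECG and a replicate within the 28-day DLT window. It would be wrong to say that QTc on KPT-8602 is unmonitored, because C1D15 is well placed.

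The counts follow directly from the calendar and dosing tables. The judgment that C1D15 resembles first exposure assumes that the half-life and Tmax reported from Study 801 also apply alongside Inqovi. How much QTc monitoring the drug needs may depend on data in the Investigator's Brochure, which the documents do not reproduce.

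**What to change.** Reconcile footnote 5 with the KPT-8602 dosing days. In Section 3.5.1, move the post-dose ECG from C1D1 to C1D8, 2 hours after the first KPT-8602 dose. Reword the footnote to: C1D8 and C1D15, 2 hours after the KPT-8602 dose, with the baseline ECG as the pre-treatment reference. No dose or dosing day changes.

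Taking the C1D8 ECG with the existing 2 h PK draw is a convenience and is not needed for any planned analysis. If the two are paired, align their windows: the ECG has +/- 20 minutes and the PK sample +/- 10 minutes.

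The cost is one calendar cell and one footnote, with the same number of ECGs and a day already attended for PK. The price is the loss of the on-Inqovi, pre-KPT-8602 ECG on C1D1 and a reference that may be about 14 days old on C1D8. If the team values the C1D1 tracing, adding a C1D8 ECG instead keeps it, at the price of one more ECG per participant.
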